We propose a randomized trial of a multifaceted intervention designed to optimize a patient-centered approach for improving adherence to prescription opioids, “Improving the Safety of Opioid Prescriptions (ISOT).” Primary care clinicians and PACT (Patient Aligned Care Team) nurses will be randomized to ISOT or the control condition; patients will be nested by clinician status. Clinicians and PACT nurses in both groups will participate in an interactive workshop on reducing prescription opioid abuse and enhancing safety. In addition, clinicians assigned to ISOT will work with a nurse care manager (NCM) who will maintain a registry of enrolled patients, track UDT administrations and results, examine state Prescription Drug Monitoring Program data, monitor medical records, and collaborate with an internist and substance abuse specialist to provide decision support when patients demonstrate evidence of prescription opioid misuse or abuse. The NCM will also meet with intervention patients to discuss strategies for reducing opioid adverse effects and preventing diversion, and to provide rationale for prescription opioid adherence monitoring. Thus, our intervention targets system, clinician, and patient levels. A research goal is to enhance patient-centered pain care and improve the quality of the communication and relationship between the patient and the primary care team pertaining to this challenging topic. The main objectives of this study are to evaluate the efficacy and acceptability of a multifaceted intervention (ISOT) to enhance opioid safety in patients with chronic pain.

SPECIFIC AIMS

Aim 1: Evaluate to what extent a multifaceted intervention (ISOT) enhances prescription opioid safety.

Hypothesis 1: At 12 months, ISOT patients will have lower rates of prescription opioid abuse, as assessed via multiple methods (self-report, clinical interview, urine drug testing), compared to patients of clinicians randomized to the control condition.

Hypothesis 2: At 12 months, ISOT patients will experience fewer adverse events (defined in this proposal to include emergency room visits, overdoses, falls, motor vehicle accidents).

Aim 2: Assess to what extent assignment to ISOT impacts pain treatment-related processes of care.

Hypothesis 1: ISOT patients will have more modifications to clinical care documented in the medical record, including more frequent UDTs and queries to state prescription drug

monitoring programs.

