Processes of Care Measures (Aim 2): At the conclusion of each patient's participation, we will extract medical record data on treatment received. This will include data in the year prior to treatment and the year during treatment on number of urine drug tests administered as part of clinical care and queries to state prescription drug monitoring programs. Results from UDTs administered as part of clinical will be extracted from VA laboratory data. For PDMP data, clinicians must provide documentation in the medical record when they check PDMP data; research staff will review medical record data of enrolled participants to evaluate incidence and frequency of PDMP checks. For patients with documented prescription opioid abuse, research staff will evaluate any potential changes in care that occurred following detection of prescription opioid abuse, including referrals to the substance abuse treatment program, mental health clinic, or specialty pain service; follow-up monitoring; and treatment changes (such as change in opioid or dose, cessation of opioids, etc.).

➤ Although the research team will monitor UDTs administered in clinical practice, these data will not be used as outcome to reflect prescription opioid abuse. UDTs will also be administered by the research team to all participants at all three research visits. These UDTs will be ordered under a unique study identification number. Patient identifying information will never be attached to or associated with these research UDT sample.

Measures of the Clinician-Patient Relationship (Aim 2): Trust in one's clinician will be examined with the Trust in Physician Scale, an 11-item self-report measure assessing interpersonal trust in patient-clinician relationships.⁸⁴ This has been used extensively as an outcome measure in prior studies examining patient-centered care and shared decision-making, and has evidenced strong psychometric properties.⁸⁵ The Participatory Decision Making Style is a brief self-report measure designed to assess level of patient involvement in medical decision making.⁸⁶ Both of these measures have been shown to be responsive to interventions directed towards by PCPs and allied health professionals.⁸⁷ The Positive Regard Scale is a recently-developed 5-item self-report measure that evaluates patients' perceptions of their relationship with their primary care provider.

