Before analyses are conducted, data will be audited for quality, including missing data patterns and evaluation of distributions with reference to planned models. The evaluation of distributions includes the detection of outliers and checking distributions of variables to ensure they meet the assumptions of planned analyses. Power calculations (below) are based on comparisons that account for data clustering. The analyses will incorporate covariate information, in particular baseline data on age, gender, depressive symptoms, history of substance use disorder (SUD), and pain intensity, which will enhance power. Analyses will be conducted with all enrolled participants regardless of attrition (intent-to-treat).

Management of Missing Data: The pattern of missingness will be examined and baseline responses compared between those with and without missing data. Variables related to missingness will be included in the analyses which should yield valid inferences.⁹⁴ We will complete sensitivity analyses comparing the main analyses results with results from analyses with completers only and based on multiple imputation.

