Clinicians will also be queried about perceived barriers and potential effectiveness of screening for prescription opioid abuse. With 32 pairs of clinicians and intra-class correlations of 0 to 0.1, we would have 80% power to detect differences of 0.50 to 0.53 SDs in mean summary scores between intervention groups.

Analyses for Aim 2: We will use GEE methods to compare between intervention groups the average numbers of clinical care documentations, UDT's, and queries to state prescription drug monitoring programs while adjusting for the baseline covariates (age, gender, depressive symptoms, history of SUD, and pain intensity) and the stratification variables. For patient level data, the approach for analysis of Aim 2 outcomes will be the same as that for Aim 1, using mixed models and/or GEE for comparisons, while adjusting for baseline covariates (age, sex, depressive symptoms, history of SUD, and pain severity), baseline measure of the outcome, and stratification variables (training type, proportion of panel prescribed opioids). Analyses will be conducted for scores on the Trust in Physician scale and Participatory Decision Making Style.

For clinician and PACT nurse data on barriers to use of UDTs, we will report descriptive information for each of the 10 questions. For each group and question, we will report the percentage of clinicians with scores at each of the five levels at baseline and follow-up, as well as the corresponding descriptive change information in follow-up scores. We will report the mean (and SD, min, max) of change for each question. We will obtain an overall survey score, by averaging the 10 question scores for each clinician and report the mean (and SD, min, max) survey score for each group at baseline and follow-up, along with the mean change (and SD, min, max) in survey score. We will use linear mixed models on the change scores to compare groups, while adjusting for clinician age, clinician training type, sex, panel size, summary survey score at baseline, and stratification variables. We will include a random pair effect to allow for correlation between the PCP and PACT nurse within each pair. P-values and 95% confidence intervals for the differences between groups in change scores will be provided. Similar analyses will be conducted for examining survey data on clinician satisfaction with ISOT.

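### Referrals, follow-up monitoring and treatment changes (Aim 2) are abstracted only after abuse is detected, and ISOT is designed to make detection more frequent

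*Combined protocol and SAP*

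**What the plan says.** Specific Aims, Aim 2, Hypothesis 1 states that "ISOT patients will have more modifications to clinical care documented in the medical record", and gives UDTs and queries to the state prescription drug monitoring program (PDMP) as examples.

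Processes of Care Measures (Aim 2) begins broadly: "At the conclusion of each patient's participation, we will extract medical record data on treatment received". Clinical UDT and PDMP counts cover the year before and the year of treatment, and records of enrolled participants are reviewed for PDMP checks. The population then narrows: "For patients with documented prescription opioid abuse, research staff will evaluate any potential changes in care". What is evaluated is "any potential changes in care that occurred following detection of prescription opioid abuse", so counting runs from detection onwards. The items listed are referrals (substance abuse, mental health, specialty pain), follow-up monitoring, and changes in treatment. No length of observation is given for this item.

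Analyses for Aim 2 uses GEE to compare between arms the "average numbers of clinical care documentations, UDT's, and queries to state prescription drug monitoring programs". The first of these three outcomes is not defined, and no denominator is given for it. The opening of Data Analysis says that everyone enrolled is analysed.

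The ISOT components include three activities that raise detection: the nurse care manager screens records for signs of non-adherence (Clinician Education and Activation, item d), may enter a UDT order when none has been done for a year, and tracks all UDT results (System Assessment and Intervention, items a and d). The Aim 2 power text expects far more UDT use under ISOT than in control.

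**The concern.** Whether a patient's referrals and treatment changes enter the data set depends on an event that follows randomisation and that the intervention promotes. Two analyses fit the text, and each has a problem.

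- **Compare arms among detected patients.** The two subsets are selected by different testing practices, so they may differ in case mix, and randomisation does not balance them.
- **Count undetected patients as zero.** The denominator stays randomised, but recording is unequal. A referral or treatment change made without documented abuse is not captured under this item, and more patients are left unobserved in the arm that tests less. ISOT can also prompt such changes itself, since the nurse care manager may flag side effects or risky prescribing without any detected abuse.

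Because the item runs from detection, earlier detection also leaves more time for changes to accrue. At stake is one component of a stated Aim 2 hypothesis. The plan bars clinical UDTs from serving as the abuse outcome, but sets no such limit on clinical detection deciding whose care is abstracted.

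**Working it through.** **Inputs from the documents.** Control patients with a follow-up UDT: 40% (Aim 2 power text). Detectable ISOT percentages: 56–61% (Table 2). Target: 32 clinicians × 5 patients = 160 per arm. Prevalence of abuse: 10–35% (Background).

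**Step 1. Table 2 reproduced.** Effective n per arm = mk / [1 + (m − 1)ICC], for m patients in each of k clinicians. Solve for p₂ in (p₂ − 0.40)√n = 1.96√[2p̄(1 − p̄)] + 0.842√[0.24 + p₂(1 − p₂)], with p̄ the mean of 0.40 and p₂ (pooled variance, two-sided 5% assumed, 80% power, no continuity correction).

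- m = 5, k = 32, ICC 0: n = 160, p₂ = 55.6% (table: 56%).
- m = 4, k = 28, ICC 0.10: n = 112/1.3 = 86.2, p₂ = 61.2% (table: 61%).

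All 16 cells agree to the whole percent. These are detectable values; the plan expects a larger difference.

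**Step 2. Size of the abstracted group.** Assume equal true prevalence, detection by clinical UDT only, a perfect test, and testing unrelated to abuse status. Expected number = 160 × prevalence × share tested.

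| Prevalence | Control, 40% | ISOT, 56% | ISOT, 61% |
|---|---|---|---|
| 10% | 6.4 | 9.0 | 9.8 |
| 20% | 12.8 | 17.9 | 19.5 |
| 35% | 22.4 | 31.4 | 34.2 |

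The ratio depends on neither prevalence nor sample size: 0.56/0.40 = 1.40 and 0.61/0.40 = 1.525 (1.52 in this text). An assumed 90% ISOT testing rate gives 0.90/0.40 = 2.25.

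**Step 3. Comparison among detected patients.** Assumptions, none from the documents: half of cases are severe; a change follows detection in 80% of severe and 30% of mild cases in both arms; ISOT testing ignores severity. ISOT then shows 0.5 × 0.8 + 0.5 × 0.3 = 0.55. Control depends on how selectively it tests:

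| Control testing, severe / mild | Control rate | ISOT − control |
|---|---|---|
| 40% / 40% | 0.55 | 0 |
| 50% / 30% | (0.40 + 0.09)/0.80 = 0.6125 | −6.25 points |
| 60% / 20% | (0.48 + 0.06)/0.80 = 0.675 | −12.5 points |
| 20% / 60% (mirror case) | (0.16 + 0.18)/0.80 = 0.425 | +12.5 points |

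Clinicians respond identically in both arms throughout, so every non-zero difference is selection.

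**Step 4. Undetected patients counted as zero.** Take 20% prevalence, unselective testing and the 0.55 change rate. Patients with a recorded change: control 160 × 0.20 × 0.40 × 0.55 = 7.0; ISOT at 56%, 160 × 0.20 × 0.56 × 0.55 = 9.9; at 61%, 10.7. This result has two explanations. If changes happen only after detection, 7.0 against 9.9 is a real effect of ISOT. If every abusing patient had the same 0.55 chance of a change whether detected or not, the true count would be 160 × 0.20 × 0.55 = 17.6 in each arm, and the difference would come from recording alone. Data abstracted by the stated rule cannot tell these apart.

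**The case against.** The strongest reply is that the plan states no analysis restricted to detected patients. The rule sits in a measures paragraph, the GEE is described as a comparison between intervention groups, and everyone enrolled is to be analysed. UDT and PDMP counts, the two components that Hypothesis 1 names, are collected for all. More detection leading to more action is also the intended pathway. Each of these statements is correct. They answer the first reading but not the second: keeping everyone in the denominator does not supply data that the abstraction rule leaves out.

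A second reply is that other record data fill the gap. The Processes of Care paragraph opens with treatment received by each patient, medication status is reviewed before research visits, and medical utilisation is extracted without a detection condition. This gives partial cover. Some opioid changes may be visible, and follow-up monitoring overlaps with the UDT and PDMP counts. The documents do not say that referrals or treatment changes will be derived from these sources.

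A third reply is that the severity figures are invented and the largest is strained. It is. At 20% prevalence and 40% tested overall, the 60%/20% row implies that 64 − 12.8 = 51.2 of 128 non-abusing controls (40%) are tested, twice the rate in mild abusers. A more coherent case tests severe patients at 60% and everyone else alike, at (64 − 9.6)/144 = 37.8%. The control rate is then (0.6 × 0.8 + 0.378 × 0.3)/(0.6 + 0.378) = 0.607, a difference of −5.7 points. The Background notes that guidelines recommend more frequent testing at higher risk, so some selectivity is plausible, but no figure for it is given.

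**Conclusion.** The point holds for referrals, follow-up monitoring and treatment changes only. Their abstraction depends on a post-randomisation event whose frequency differs by design between arms, by a factor of 1.40 to 1.52 at Table 2's detectable testing rates. That factor rests on equal true abuse, detection by clinical UDT alone and a perfect test. Chart monitoring under ISOT is a further route to detection that it leaves out.

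A reader might infer that the whole Aim 2 comparison of care modifications is non-randomised. The documents do not support that, because the UDT and PDMP counts cover every enrolled patient and are compared by randomised arm. Nor does ISOT create the detected group: 40% of controls are assumed to be tested, so ISOT enlarges the group and may alter its make-up. A fixed deficit against ISOT cannot be inferred either, since the subset bias may be zero or of either sign depending on how selectively controls are tested.

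This should be corrected. It affects one component of a secondary aim and leaves the primary outcome untouched, but changes that were never abstracted cannot be recovered by modelling.

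**What to change.** 1. In Processes of Care Measures (Aim 2), abstract referrals, follow-up monitoring and treatment changes for every enrolled patient, whether or not abuse was detected, over the same 12-month window from enrolment. Score zero only when the chart has been reviewed and none is found.
2. In Analyses for Aim 2, define "average numbers of clinical care documentations" as these counts, with all enrolled patients as the denominator, and compare arms by the GEE already planned.
3. Report results among patients with detected abuse descriptively, with the number detected in each arm, and state that this subset is formed after randomisation.

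The cost is a wording change and some added chart abstraction, on records already reviewed for UDT and PDMP data.

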Common adverse effects associated with opioid initiation include constipation, nausea, somnolence, and vomiting²³ and up to 50% of patients discontinue opioids due to intolerance or insufficient pain relief.^{17,23} Patients maintained on COT may be exposed to additional adverse effects, including psychosocial and medical harms.²⁴ Opioids are associated with increased likelihood of cardiovascular events, fractures, hypogonadism, sleep-related breathing disorders, and death.⁷ Unintentional overdose deaths quadrupled between 1999 and 2007, and in 16 U.S. states, more people die from prescription opioid overdose than automobile accidents.²² The dose of opioids is a major contributing factor in adverse effects^{3,4,6} and recent studies highlighted the relationship between opioid dose and elevated risk of overdose death.^{2,5}

Attempts to Reduce Harms from Prescription Opioids: Empirical studies and consensus guidelines support the routine use of urine drug tests (UDT) to assess adherence and screen for prescription opioid abuse among patients prescribed COT.²⁵⁻²⁷ The 2010 Department of Veterans Affairs Guidelines for treatment of patients prescribed COT recommend UDTs for all patients prior to initiating COT and periodic testing in stable patients. Increased frequency of UDT is recommended for patients at higher risk of abuse.¹¹ These recommendations were highlighted by recent reports from the VA Office of Inspector General and Under Secretary for

Health.²²

Despite common calls for routine screening, regular UDT is uncommon. In prior research, we demonstrated that 26% of VA patients prescribed COT receive a UDT in a one year period.²¹ Among patients at higher risk for prescription opioid abuse (such as patients with a substance use disorder), less than half receive UDT.²¹ These data replicate findings from other settings indicating UDTs are infrequently used.^{12,28-30}

Clinicians who routinely utilize UDT for all patients will encounter aberrant results in up to 40% of tests.³¹ Even among patients who appear compliant with COT, approximately 20% will test positive for an illicit drug or another non-prescribed opioid.²⁶ These findings suggest clinicians over-estimate their ability to predict risk for prescription opioid abuse. Aberrant UDT results provide an opportunity to initiate discussions about treatment adherence and may lead to safe and appropriate changes in treatment.

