
assigned to work with must also participate. **Patients:** All patients enrolled in primary care clinics will be potentially eligible.

Inclusion Criteria: Participants must be enrolled in primary care at the VAPORHCS and be receiving chronic opioid therapy for chronic pain unrelated to a life-limiting disease. Chronic opioid therapy is defined as receiving an opioid prescription in three consecutive months or six prescriptions in the last year with a current prescription.²⁰ The only other inclusion criterion is the ability to read and write in English. **Exclusion Criteria:** Age younger than 18 years, opioid therapy for palliative or end-of-life care, current enrollment in an opioid substitution program, or lack of telephone access. In order to identify potentially-eligible patients, we will request a waiver of informed consent, to access clinical diagnostic and pharmacy data. These data will be obtained for VA patients from the Corporate Data Warehouse, which will be accessed and analyzed within the secure user-restricted VINCI study site workspace.

Recruitment: **Clinicians:** PCPs and PACT nurses will be recruited through email, discussions at practice meetings (the PI or a member of the research team will make a presentation during a weekly staff meeting and/or during the monthly meeting for all PCPs), and direct contact by the investigators. **Patients:** We will ask participating PCPs for permission to recruit patients. Using data from the electronic medical record, we will identify patients at the VAPORHCS who potentially meet our inclusion/exclusion criteria. Consistent with the VAPORHCS's policy on recruiting participants for research studies, we will include a signed letter from the clinic manager where the patient receives his/her primary care, or director of primary care. The information sent to patients will include an accompanying letter from the research team, which will describe the study and invite patients to participate in a telephone screening session. Patients will be asked to return enclosed addressed and stamped letters, or to call our research office telephone number if interested in being screened.

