Measures of Prescription Opioid Misuse/Abuse (Aim 1): The primary outcome will be responses to the Current Opioid Misuse Measure (COMM), a 17-item self-report measure that assess several constructs that place individuals at risk of opioid misuse and abuse.⁸⁰ The COMM has been well-validated⁸¹ and previously used in treatment outcome studies.³³ The COMM has also been validated for detecting prescription opioid abuse using cut-off scores ≥ 13 .⁸² The Timeline Followback (TLFB; Sobell & Sobell, 1992) is a frequently used assessment method that uses calendar prompts to elicit frequency and intensity of substance use within a specific timeframe. The TLFB has demonstrated good test-retest reliability and validity for assessing multiple substances at one time (Ehrman & Robbins, 1994; Fals-Stewart et al., 2000). This study will assess use of alcohol, marijuana, methamphetamine, cocaine, heroin, opioid medications, and other prescription medications in the past 30 days. The Structured Clinical Interview for DSM-IV(SCID) will be used to assess current alcohol and substance use disorders.⁸³ The Overdose Risk Behavior (ORB) questionnaire is a newly-developed 14-item self-report measure that assesses behaviors and activities that place an individual at higher risk of accidental overdose to prescription opioids. Participants will complete Urine Drug Tests, to evaluate for the presence of substances ingested by participants. UDTs will evaluate for cannabis, cocaine, amphetamines, benzodiazepines, barbiturates, opioids, and opiates. Confirmatory testing will be conducted for all UDT screens with unexpected results. The purpose of UDT is to have confirmation of certain prescribed and illicit substances that have been ingested by study participants. Research staff will review medical record data prior to research visits to confirm medication status. Participants will be asked to validate pharmacy data about prescription status, as well as medications prescribed outside VA.

Measures of Opioid-Related Adverse Events (Aim 1): Prior to appointments, research staff will review medical record data for participants to track adverse effects. This includes emergency room visits, falls, and overdoses. Participants will also be queried about these effects and motor vehicle accidents at each research visit.

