observations on different patients of the same PCP and for repeat observations on the same patient. Transformations of the outcome will be applied to meet distributional assumptions. In linear mixed models, we will include baseline measures of patient age, sex, depressive symptoms, history of SUD, and pain severity as covariates. We will also adjust for baseline COMM score and the stratification variables: PCP training type (MD/DO vs NP or PA) and proportion of clinician panel prescribed opioids (high vs low). In addition to testing formal hypotheses, we will report 95% confidence intervals for the differences in mean outcomes between groups at 6 and 12 months. For comparing the percentages classified as abusing opioids at any time during follow-up (combining information from 6 and 12 months) based on SCID and UDT, we will use generalized-linear mixed models (or GEE as needed) to incorporate correlation between patients of the same PCP. We will adjust for baseline measures of the outcome along with the covariates listed above. We will report group comparisons on all three primary outcomes (COMM, SCID, and UDT). Assuming 15% of the sample has current SUD (consistent with other research), we will not conduct interaction analyses, but will present descriptive information for each outcome (COMM, SCID, UDT) on treatment outcomes by SUD status.

Data on opioid-related adverse events will be obtained from the medical record and participant self-report. We will collect data on opioid overdoses, falls, motor vehicle accidents, and ER visits related to pain. Descriptive information on opioid-related events will be provided for each group (numbers and percentages of participants with each event). Because the number of adverse events is expected to be small, we will use Fisher's Exact test to compare adverse event percentages between groups. We will compare both percentages for each individual type of event as well as percentages of individuals experiencing any adverse event between groups.

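### The adverse-event comparison (Aim 1, Hypothesis 2) uses neither baseline opioid dose, which the plan itself names as a driver of harm, nor the PCP clustering; a supportive any-event model would use both

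*Combined protocol and SAP*

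**What the plan says.** **Dose as a risk factor.** The Background states: "The dose of opioids is a major contributing factor in adverse effects". It also cites work relating dose to overdose death.

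**Eligibility.** Chronic opioid therapy means "receiving an opioid prescription in three consecutive months or six prescriptions in the last year with a current prescription". This counts prescriptions and sets no dose limit.

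**Pharmacy data.** The Inclusion Criteria section plans a waiver of consent "to access clinical diagnostic and pharmacy data" so that potentially eligible patients can be found. Under Study Measures: "Participants will be asked to validate pharmacy data about prescription status, as well as medications prescribed outside VA". Neither place defines a dose variable. In the methods, dose appears only as a process of care after abuse has been detected, under "treatment changes (such as change in opioid or dose, cessation of opioids, etc".

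**Covariates.** The Data Analysis section names "baseline data on age, gender, depressive symptoms, history of substance use disorder (SUD), and pain intensity, which will enhance power". Analyses for Aim 1 repeats the set: "we will include baseline measures of patient age, sex, depressive symptoms, history of SUD, and pain severity as covariates". It adds the baseline COMM score and the two stratification variables, PCP training and whether a high or low share of the panel is on opioids. The Aim 2 and Aim 3 lists have the same five patient factors.

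**Adverse events.** Analyses for Aim 1 compares each event type, and the percentage with any event, by Fisher's exact test, because few events are expected.

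**Order of events.** Under Randomization, PCPs are allocated before patients are recruited, and research assistants are blind to allocation. Under Recruitment, PCPs are asked for permission to approach their patients, who then opt in by letter or telephone.

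**The concern.** Hypothesis 2 of Aim 1 predicts fewer adverse events under ISOT. It is tested by the one patient-outcome comparison in the plan that uses no baseline information, and dose is the risk factor that the plan itself ties to those events. The same test treats patients as independent, although PCPs are the randomised units and every power table allows for clustering.

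Two things follow. First, a prognostic factor that could be measured is left in the noise of a comparison that already has few events. Second, allocation of PCPs does not fix which patients later enrol. If dose affected PCP permission or patient opt-in differently in the two arms, the arms would differ systematically in dose. Neither permuted blocks nor a confidence interval deals with that. With no plan to derive dose or report it by arm, any adjustment would have to be chosen after the data were seen.

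**Working it through.** **1. The plan's own figure.** Inputs, all from the Aim 1 power section: SD of COMM change 8.9, 80% power, α 0.05 (taken as two-sided), 28 or 32 PCPs per arm, 4 or 5 patients each, ICC 0 to 0.10.

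- Design effect DE = 1 + (m − 1) × ICC. For 32 × 5 at ICC 0.02: 1 + 4 × 0.02 = 1.08.
- SE = 8.9 × √(2 × 1.08/160) = 1.034.
- Detectable difference, normal formula: (1.960 + 0.842) × 1.034 = 2.90. A noncentral t with 62 cluster-level degrees of freedom gives 2.94. Table 1 has 2.9.
- The noncentral t reproduces all 16 cells of Table 1 after rounding. So the plan's power figures stand, and they include clustering.

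**2. Chance imbalance in baseline dose, in SD units.** The documents give no ICC for dose, so the ICCs of Tables 1 and 2 are used. SE = √(2 × DE/n per arm).

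| Design | ICC | DE | n per arm | SE | 95% range |
|---|---|---|---|---|---|
| 32 × 5 | 0.02 | 1.08 | 160 | 0.116 | ±0.23 |
| 28 × 4 | 0.10 | 1 + 3 × 0.10 = 1.30 | 112 | 0.152 | ±0.30 |

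A higher ICC for dose would widen these ranges.

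**3. What such a difference does to event risk.** The documents give neither event rates nor dose–event associations. Assumed: control risk 5% to 20%, odds ratio 1.3 to 2.0 per SD of dose, no effect of ISOT. Risk in the higher-dose arm = average of 1/(1 + exp(−[a + ln(OR) × (X + d)])) over X ~ N(0, 1), where d is the imbalance and a is set so that d = 0 gives the control risk.

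| Control risk | OR per SD | Shift at d = 0.2 | Shift at d = 0.3 |
|---|---|---|---|
| 5% | 1.3 | 0.25 points | 0.39 points |
| 5% | 2.0 | 0.68 | 1.05 |
| 10% | 1.3 | 0.48 | 0.73 |
| 10% | 2.0 | 1.25 | 1.93 |
| 20% | 1.3 | 0.84 | 1.27 |
| 20% | 2.0 | 2.14 | 3.26 |

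For scale, the 95% half-width of a risk difference with 160 per arm, ignoring clustering, is 1.96 × √(2p(1 − p)/160). This is 4.8 points at p = 5% and 8.8 points at p = 20%. At 10% risk, Fisher's test rejects in 3.3% of trials with equal risks, and in 5.9% if a systematic difference makes the risks 10% and 11.9%.

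**4. Clustering in Fisher's test.** The standard error implied by independent patients is too small by √DE: √1.08 = 1.04 at ICC 0.02 (32 × 5) and √1.30 = 1.14 at ICC 0.10 (28 × 4). The ICC for adverse events is not given. The conservatism of Fisher's test (3.3% above) offsets part of this.

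**5. Dose in the COMM model.** With an assumed partial correlation r between dose and COMM change, the detectable difference becomes 2.90 × √(1 − r²): 2.88 at r = 0.1, 2.84 at r = 0.2, 2.76 at r = 0.3.

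**The case against.** The strongest reply is that chance imbalance is not bias. Randomisation makes the comparison valid whatever the arms look like on dose, and the error rates already allow for such differences. The Randomization section also argues that blocking and many clusters guard against major imbalance. This stands. A reader might infer that the ±0.23 to ±0.30 SD range measures bias in the result, and it does not.

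Three other strong readings also fail.

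- *Dose is the factor most likely to be unbalanced, because it follows the prescriber.* This is plausible, but the documents give no ICC for dose and no comparison with other factors.
- *Nothing in the analysis could reveal an imbalance.* The general covariate sentence is worded as a selection, variables related to missingness may enter the models, and the title page refers to a separate publication for the final protocol and recruitment outcomes. Dose is not prespecified; more than that cannot be said.
- *Every covariate list needs dose.* The documents link dose to adverse effects and overdose death, not to the Aim 2 or Aim 3 outcomes. In the COMM, SCID and UDT models, the baseline outcome, pain and SUD history would absorb part of any dose effect.

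Selective enrolment is also only a possibility. Staff are blind and candidates are found from records. What remains open is PCP permission, whose timing relative to allocation is not stated, and patient opt-in.

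Finally, few events are expected, so a clustered adjusted model may be unstable. That is a reason to restrict the model to the any-event outcome and keep it supportive. It is no reason to leave dose unreported.

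**Conclusion.** The point holds for Aim 1, Hypothesis 2, as a low-cost improvement. The plan calls dose a major factor in adverse effects and has access to pharmacy records, yet compares adverse events with a test that uses neither dose nor the clusters.

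The size is modest. A 0.2 to 0.3 SD dose difference moves the event risk by 0.3 to 3.3 percentage points on assumed risks of 5% to 20% and odds ratios of 1.3 to 2.0 per SD. That is well inside the sampling uncertainty. If the difference arises by chance, the loss is one of precision. It would be bias only if enrolment after PCP randomisation differed by dose between arms, which the documents allow but do not show. For COMM the gain from adjustment is small (2.90 to between 2.88 and 2.76, on assumed correlations of 0.1 to 0.3).

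**What to change.** 1. Define baseline prescribed opioid dose from the pharmacy data, with the conversion and time window fixed in advance. Where possible the window should end before the PCP's randomisation. A window tied to patient enrolment could fall after ISOT PCPs have met the nurse care manager, so that dose already reflects the intervention. If a pre-randomisation window is impractical for some patients, run both windows.
2. Report baseline dose by arm.
3. For the any-adverse-event outcome, add a prespecified supportive model beside the planned Fisher's test. It should account for PCP clustering and adjust for dose and the two stratification variables. Do not extend it to single event types, where events may be too few. State in advance what is reported if the model does not converge.
4. Optionally, add dose to the COMM, SCID and UDT models as a sensitivity analysis. No change to the Aim 2 and Aim 3 lists is needed.

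The cost is SAP wording and one derived variable, which must be defined and extracted because the documents show access to pharmacy data but no dose variable. Doses prescribed outside VA will be measured with some error, though participants are already asked about outside medications. The model may be unstable if events are sparse. Adjustment for dose also cannot correct selective enrolment on other, unmeasured factors.
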